Following identification of the optimal dose subjects will undergo a washout period of no less than 2 and no more than 10 days. The minimum 2-day washout was chosen because of the known 2- to 3-hour plasma half-life of droxidopa. [17]

Study 2 – To determine the effect of droxidopa, compared to placebo, on: 2.1A) supine SBP (mmHg); 2.1B) proportion of supine BP observations \geq 140/100 mmHg; 2.2) SBP during a HUT and 2.3) change in CBFv from supine to HUT. Within about 1 week of determining the dose of droxidopa that normalizes seated SBP eligible participants will return to the laboratory for the placebo-controlled randomization trial. Subjects will arrive at the laboratory between 10AM and 1PM after a light breakfast and having avoided alcohol, caffeine, and nicotine for 12-hours. Subjects will remain in their wheelchair for instrumentation, which will include: 1) ECG, 2) brachial BP, 3) finger arteriolar BP and 4) CBFv. After instrumentation subjects will be transferred to the supine position (on the tilt table) for a 10-minute period of quiet rest and baseline supine data collection. Participants will then be administered either oral droxidopa or matching placebo in a double-blinded manner and will remain in the supine

position for 60 minutes. Supine HR, finger BP and CBFv will be monitored continuously for 5-minutes at 0, 25 and 55 minutes, supine brachial BP will be monitored and recorded at 0, 10, 20, 30, 40, 50 and 60 minutes. The HUT maneuver will be initiated 60 minutes post-droxidopa/placebo

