Secondary Aims: To determine the effect of the individualized optimal dose of droxidopa, compared to placebo, on (1) supine BP (**Safety #2**), (2) SBP during a head-up tilt (HUT) maneuver to 70° (**Efficacy #2**) and change in cerebral blood flow velocity (CBFv) from supine to HUT (**Efficacy #3**). The following hypotheses will be tested in hypotensive individuals with SCI:

- **Hypothesis 2.1A** – Average supine SBP will be significantly increased following droxidopa administration compared to placebo.
 - This hypothesis will be tested using a repeated measures analysis of covariance where the pre-droxidopa or placebo SBP will be used as the covariate and the adjusted post-test scores will serve as the dependent variable. In addition, the covariate adjusted point estimate and 95% confidence interval of the difference between drug conditions will provide the first reported estimate of the supine SBP response to droxidopa versus placebo in the SCI population.
- **Hypothesis 2.1B** – The proportion of supine BP observations $\geq 140/100$ mmHg following droxidopa administration will not differ significantly from the proportion observed during the placebo trial.
 - This hypothesis will be tested by performing separate (one each for systolic and diastolic pressure) tests of the differences between dependent proportions, from which the 95% confidence intervals will be calculated. The presence of zero in a confidence interval will indicate a lack of statistical difference in incidence of hypertensive events between the droxidopa and placebo conditions.
- **Hypothesis 2.2** – Average SBP during 70° HUT will be significantly increased following droxidopa administration compared to placebo.
 - This hypothesis will be tested by performing a dependent t-test between the mean SBP during 70° HUT comparing droxidopa to placebo. Further, the point estimate and resulting 95% confidence interval will provide an estimate of the SBP response to HUT of droxidopa versus placebo in the SCI population.
- **Hypothesis 2.3** – The change in CBFv from supine to HUT will be significantly attenuated following droxidopa administration compared to placebo.

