 - This hypothesis will be tested using a repeated measures analysis of covariance where the pre-HUT CBFv will be used as the covariate and the adjusted post-HUT CBFv scores will serve as the dependent variable. In addition, the covariate adjusted point estimate and 95% confidence interval of the differences between drug conditions (droxidopa vs. placebo) will provide the first reported estimate describing the effect of droxidopa on the CBFv response to HUT.
- **Hypothesis 2.4** – Plasma renin and serum aldosterone concentrations will be reduced and plasma norepinephrine concentrations will be increased during HUT following administration of droxidopa compared to placebo.
 - These hypotheses will be tested using a repeated measures analysis of covariance where the pre-HUT concentrations will be used as the covariate and the adjusted post-HUT concentrations will serve as the dependent variable. In addition, the covariate adjusted point estimate and 95% confidence interval of the differences between drug conditions (droxidopa vs. placebo) will provide the first

reported estimate describing the effect of droxidopa on these vasoactive substances in response to HUT.

Safety Monitoring:

As is stated in the consent forms there is a risk of increased systemic blood pressure following administration of droxidopa.

Laboratory Monitoring: During the laboratory observation heart rate and blood pressure will be closely monitored at 15 minute intervals and action will be taken if blood pressure is elevated above 140/90 mmHg for more than 30 minutes. The action plan to lower blood pressure in the laboratory is as follows:

1. Loosening of clothing or braces
2. Re-positioning the participant in his/her wheelchair
3. Emptying of the bladder/catheter bag

If these measures prove unsuccessful in lowering blood pressure the study physician will be alerted and brought to the laboratory for further subject monitoring and administration of an anti-hypertensive agent if deemed necessary. The medication of choice will be sub-lingual nitroglycerin.

The study clinician, [name] will monitor and review all blood pressure recordings during each laboratory visit in both Study 1 and 2. Although he will not be in the laboratory for the duration of testing, his office is across the hall and he is readily accessible if needed.

Testing will be scheduled when [name] is in the office only.

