IND number or other status (submit validation or correspondence): **137213**

If there is no IND number, is there an FDA exemption? (If yes, please submit FDA correspondence.)? **See attached FDA IND letter.**

YES	X	NO	
-----	---	----	--

d. Will investigational devices be used:

No.

Is there an IDE issued by the FDA? **N/A**

YES		NO	
-----	--	----	--

IDE number or other status (submit validation or correspondence):

Is there an abbreviated IDE?

YES		NO	
-----	--	----	--

If there is no IDE number, is there an FDA exemption? (If yes, please submit correspondence with FDA.)?

YES		NO	
-----	--	----	--

How would you determine the risk-benefit analysis for investigational devices?

e. Risks for Investigational Drugs/Device:

For investigational drugs, what are the possible risks associated with the study drug relative to possible interactions with medications likely to be used by subjects? **Following droxidopa, administration BP may elevate above the normal range (>140/90 mmHg). In addition, symptoms of autonomic dysreflexia (AD) may become frequent or worsen while taking the study medication. Clinical staff will assist the subject to an upright seated position, loosen any tight clothing or braces that the subject is wearing and may check and empty your bladder and bowel. If BP remains high for more than 30 minutes the subject will be provided with a medication to lower their pressure. The medication of choice will be a nitropaste (Nitroglycerin Ointment, 2%) that will be placed one inch on the subjects forehead.**

Droxidopa risks ($\leq 8\%$ likely) include: slow or fast heartbeat, pounding in the ears, low back or side pain, and nervousness.

Since this research may have unknown effects on an unborn child and should not be done during pregnancy, it is necessary for a pregnancy test to be done first. To your knowledge you are not pregnant at the present time. You also agree to avoid becoming pregnant (use contraceptives, take precautions against becoming pregnant, etc.) during this study.

As with any research, there may be unforeseen risks and discomforts. A medical doctor associated with the study will be available to treat any medical emergency that may develop.

What will your approach be to such risks? **Study personnel and clinical staff will monitor BP daily during the study participation period.**

Will such subjects be excluded from the study? **No.**

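### Three passages conflict on what to do when blood pressure rises in the Study 2 supine hour, and the plan has no rule for supine readings lost as a result

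*Protocol*

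**What the plan says.** **Measurement schedule** (Protocol, Research Design and Methods, Study 2). After dosing, "Participants will then be administered either oral droxidopa or matching placebo in a double-blinded manner and will remain in the supine" position for 60 minutes, and "supine brachial BP will be monitored and recorded at 0, 10, 20, 30, 40, 50 and 60 minutes". Head-up tilt starts 60 minutes after dosing. No exception is given for raised BP.

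**Risk response** (Combined protocol and SAP, item 15(e)). If BP rises above 140/90 mmHg after droxidopa, or autonomic dysreflexia symptoms become more frequent or worse, "Clinical staff will assist the subject to an upright seated position, loosen any tight clothing or braces that the subject is wearing". That step has no waiting time. Only the drug step does: "If BP remains high for more than 30 minutes the subject will be provided with a medication to lower their pressure".

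**Laboratory plan** (Protocol, Safety Monitoring, Laboratory Monitoring). Here "action will be taken if blood pressure is elevated above 140/90 mmHg for more than 30 minutes". One of the three measures is "Re-positioning the participant in his/her wheelchair". Nothing addresses a participant lying on a tilt table.

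**Analysis** (Protocol, Data Analysis; Combined protocol and SAP, item 17a). Hypothesis 2.1A compares average supine systolic BP (SBP). Hypothesis 2.1B states that the proportion of supine observations at or above 140/100 mmHg "will not differ significantly from the proportion observed during the placebo trial". Systolic and diastolic pressure are tested separately, and a 95% confidence interval containing zero is read as no difference. Neither document says how supine readings missing after an early exit are handled, or whether 2.1B pools observations or averages per-subject proportions.

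**The concern.** The supine hour produces Safety #2. Under item 15(e) a raised reading can end the supine series, so missing readings depend on the outcome being measured. If droxidopa raises supine BP this happens mainly on droxidopa visits, although the rule applies equally on placebo visits. Both supine hypotheses are computed from whatever was recorded supine. With a sustained rise, the lost readings would have been high, so 2.1A and a pooled 2.1B can be too low on drug. For 2.1B that moves the estimate towards the hypothesised absence of a difference.

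The tilt is also affected. The plan does not say whether it goes ahead after a participant has been sat up or given a BP-lowering drug. Hypotheses 2.2, 2.3 and 2.4 all assume a tilt that follows the undisturbed supine hour. With three sites, practice could differ from site to site.

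**Working it through.** The plan gives no expected supine hypertension rate and no power calculation, so there is no figure of its own to reproduce. Two checks were made.

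**1. Counts on the seven-reading schedule.** Inputs from the Protocol: readings at 0, 10, 20, 30, 40, 50 and 60 minutes. Assumption: BP becomes high at the stated reading and stays high. Proportion = high readings recorded / readings recorded.

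| Rise starts (min) | All seven kept | Exit at first high reading (item 15(e)) | Exit after 30 min high (Laboratory Monitoring) |
|---|---|---|---|
| 10 | 6/7 = 86% | 1/2 = 50% | 4/5 = 80% to 5/6 = 83% |
| 20 | 5/7 = 71% | 1/3 = 33% | 4/6 = 67% to 5/7 = 71% |
| 30 | 4/7 = 57% | 1/4 = 25% | 4/7 = 57% |
| 40 | 3/7 = 43% | 1/5 = 20% | 3/7 = 43% |
| 50 | 2/7 = 29% | 1/6 = 17% | 2/7 = 29% |
| 60 | 1/7 = 14% | 1/7 = 14% | 1/7 = 14% |

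The range in the last column is action at exactly 30 minutes versus at the first reading beyond it. The loss there is 0 to 2 readings.

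The opposite case is one isolated high reading at minute 20: 1/7 = 14% in full, 1/3 = 33% if the series stops there.

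*Effect on the mean* (assumed SBP 120, 120, 145, 150, 155, 155, 150). Full: 995/7 = 142.1. Stopped at minute 20: 385/3 = 128.3. Difference: 13.8 mmHg.

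*Group level.* Assume k of 30 participants follow this course on droxidopa and nobody else has a high reading (30 is the Combined protocol and SAP figure; the Protocol anticipates 25).

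- k = 3: the mean falls by 13.8 × 3/30 = 1.4 mmHg. The pooled proportion goes from 15/210 = 7.1% to 3/(27 × 7 + 3 × 3) = 3/198 = 1.5%. The per-subject average falls by (0.714 − 0.333) × 3/30 = 3.8 points.
- k = 1 to 6: the mean falls by 0.5 to 2.8 mmHg and the per-subject average by 1.3 to 7.6 points.

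**2. Simulation, 200,000 subjects per scenario.** Every input is an assumption: baseline supine SBP 118 (SD 13), anyone at or above 140 at time 0 excluded, linear mean rise by minute 60 of 0, 10, 20 or 30 mmHg (SD 0, 10, 15, 15), reading noise SD 5 or 10, autocorrelation 0 or 0.7, systolic threshold only.

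- Mean rise 10 to 30, exit at the first high reading: the pooled proportion is 4.1–14.4%, against 9.5–31.1% with all readings. Average SBP is 0.7 to 5.3 mmHg lower.
- Same rises, 30-minute rule: the pooled proportion falls by at most about 2 points.
- Droxidopa minus placebo (rise 20 versus 0, noise SD 10, no autocorrelation): 21.9 − 5.2 = 16.7 points in full, 10.4 − 3.3 = 7.1 points with exit at the first high reading. For average SBP, 126.01 − 116.06 = 9.95 mmHg becomes 123.10 − 116.34 = 6.76 mmHg.
- No rise, noise SD 10, no autocorrelation: the per-subject proportion goes up, from 5.2% to 6.6%.

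**The case against.** The best defence is that a measurement schedule and a conditional safety response do not contradict each other: any schedule yields to safety. Item 15(e) is a drug-risk answer on an ethics form, names neither study nor posture, and is partly in consent-form language. The Protocol's laboratory plan may be the operative one, and under it few readings are lost. Two of its three measures do not require leaving the supine position.

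The documents' own data do not point to prolonged elevation. At 400 mg, three people each had one seated SBP at or above 140 in the first 30 minutes, 3% of recordings, and the Protocol reports limited supine or seated hypertension at that dose. Screening also excludes sustained supine elevation. These are secondary aims in a pilot with no powered effect size.

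Most of this stands as a limit on size. It does not close the gap. Nothing says which passage governs the supine hour, and neither document has a rule for the lost readings under either trigger. Supine elevation is also plausible. Eligibility may rest on a supine-to-seated fall of at least 20/10 mmHg, while the dose is chosen on seated SBP up to 139. A participant brought to 125 seated who kept a 20 mmHg fall would be at 145 supine.

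A reader might infer that supine readings stop in exactly the people with supine hypertension. They need not: the trigger is 140/90 or dysreflexia symptoms, while the endpoint is 140/100, so some people sat up would never meet the endpoint. Nor are readings lost from the drug condition only, because treatment is double-blind and the same rule applies on placebo visits.

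**Conclusion.** The conflict between the three passages is real, and so is the missing analysis rule. If item 15(e) is followed and droxidopa produces a sustained supine rise, average supine SBP and the pooled hypertensive proportion can be understated, and for 2.1B the error favours the planned safety conclusion. For one affected visit with a rise from minute 20, the proportion is 33% instead of 71%. In the simulation, the pooled proportion was roughly halved.

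The stronger inference, that Safety #2 is understated, is not supported. Under the 30-minute rule the loss is 0 to 2 of 7 readings. A single transient high reading can overstate a per-subject proportion (1/7 to 1/3). A summary of whether any reading crossed the threshold would be unaffected when exit follows the first reading at or above it, because that reading is recorded. The size depends on the course of BP, the number affected and the rule staff follow, none of which the documents give. The point is worth correcting before Study 2 data are analysed, but it concerns secondary outcomes only.

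**What to change.** - **Reconcile the passages.** The Protocol's Study 2 description, its Laboratory Monitoring plan and item 15(e) should agree on what happens to the supine hour and the tilt when BP is acted on. The last two also differ on the form of the BP-lowering drug. The clinical steps are for the investigators to choose.
- **Record and report.** Capture the time and reason of any BP-lowering action or early exit from supine, and tabulate these by condition.
- **Define 2.1B.** State whether it is pooled or per subject.
- **Analyse.** Keep the observed-data analyses of 2.1A and 2.1B, and pre-specify a conservative sensitivity analysis beside them. For 2.1B, count supine readings lost after such action as hypertensive only in the test (systolic 140, diastolic 100) whose threshold was met at exit. For 2.1A, carry the last supine SBP forward to minute 60. The 2.1B rule should not be the main analysis: it would score the transient case 5/7 when the truth is 1/7. Carrying forward is not a strict bound if BP is still climbing: in the example it gives (120 + 120 + 5 × 145)/7 = 137.9, against a true 142.1.
- **Tilt outcomes.** Repeat 2.2, 2.3 and 2.4 without tilts begun after such action.

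The cost is wording, a time-and-reason entry on the case report form and a little extra analysis. The supine safety result may look slightly less favourable to droxidopa.

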Study 1– To determine the proportion of subjects with SCI with: 1.1) a normotensive response to droxidopa and 1.2) a sustained hypertensive response to droxidopa. The dose optimization study will be scheduled to begin after completion of the screening visit. Eligible participants will be administered oral droxidopa in a dose escalation, open-label manner beginning with 200 mg. The dose will be adjusted upwards by 100 mg on subsequent visits until (1) average SBP recorded 60-120 minutes after dose administration is 111-139 mmHg in males and 101-139 mmHg in females (i.e., normotensive), (2) sustained elevation (\geq 30 consecutive minutes) in seated SBP \geq 140/100 mmHg, (3) maximum dose of 800 mg is reached without adequate SBP response or (4) intolerable side effects considered related to study medication. Subjects will visit the testing laboratory on as few as 1 (200 mg) and as many as 8 (800 mg) days, and will be asked to refrain from taking prescription anti-hypotensive agents for 12 hours prior to study. Participants with an excessive response to the 200mg dose, i.e., average 4-hour SBP above 139, will be asked to visit the laboratory to determine their blood pressure response to a 100mg dose. Based on our previous data, we do not anticipate an excessive response to the 200mg dose in most participants, we request the addition of the 100mg dose be administered only in participants with excessive responses to the 200mg dose. Subsequent study visits will be scheduled no less than 2 and no more than 10 days apart. Subjects will arrive at the laboratory between 10AM and 1PM after a light breakfast and having avoided alcohol, caffeine, and nicotine for 12-hours. Subjects will remain in their wheelchair for instrumentation, which will include: 1) 3-lead electrocardiogram (ECG) for continuous recording of heart rate (HR) and respiration rate; 2) brachial BP, which will be monitored using a manual sphygmomanometer and finger arteriolar beat-to-beat BP, which will be recorded using photoplethysmography with a cuff placed around the middle or index finger of the left hand. Seated cardiovascular hemodynamic assessments will be monitored and recorded at 15-minute intervals for 4-hours, and the side effects questionnaire (Appendix 4) will be administered hourly during the 4-hour study. Individuals who do not respond to droxidopa with a normal seated SBP will be excluded from Study 2. Each study visit will take about 5 hours.

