This is a pilot trial to determine the dose efficacy and safety of droxidopa to increase systemic BP and improve orthostatic BP and CBFv responses compared to placebo in hypotensive individuals with SCI. Because this is a pilot trial, the following statistical analyses are not powered for a specific effect size; however, the results will be used to power a subsequent large scale clinical trial to identify the utility and safety of droxidopa for treatment of asymptomatic hypotension in persons with SCI.

Primary Aim 1.1: Dose optimization, open-label trial to determine the proportion of subjects with SCI with a normotensive response to droxidopa (**Efficacy #1**). Normotension will be defined as an average systolic BP (SBP) recorded 60-120 minutes after dose administration of between 111-139 mmHg in males and 101-139 mmHg in females.

- **Hypothesis 1.1** – Seated SBP will be normalized in 60% of the study sample following administration of droxidopa.
 - This hypothesis will be tested by constructing a 95% confidence interval about the sample proportion of cases in which BP is normalized with droxidopa. The inclusion of the 60% value in the confidence interval will be taken as evidence in support of the hypothesis. Further, the point estimate and confidence interval will provide the first reported estimate of the BP normalizing effect of droxidopa in the population with SCI.

Primary Aim 1.2: Dose optimization, open-label trial to determine the proportion of subjects with SCI with a hypertensive response to droxidopa (**Safety #1**). Hypertension will be defined as a sustained elevation in seated SBP \geq 140/100 mmHg or intolerable side effects considered related to study medication

- **Hypothesis 1.2** – Less than 10% of the study sample will exhibit hypertension or intolerable side effects related to administration of droxidopa.

- This hypothesis will be tested by constructing a 95% confidence interval about the proportion of cases in which either seated BP $\geq 140/100$ or intolerable side effects occur. If the 95% CI excludes values $\geq 10\%$, this will be taken as evidence in support of the hypothesis. Further, the point estimate and confidence interval will provide the first reported estimate of the expected side effects of droxidopa treatment in the population with SCI.

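### The decision rules for H1.1 and H2.1B reward imprecision: a 95% CI only has to contain 60%, or zero, for the favourable verdict to follow

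*Protocol*

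**What the plan says.** The rules stand in the Protocol, Data Analysis, and again in the Combined protocol and SAP, item 17.

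- **H1.1 (Efficacy #1)** is a point statement: "Seated SBP will be normalized in 60% of the study sample following administration of droxidopa". Its test is a 95% CI for the proportion, and "The inclusion of the 60% value in the confidence interval will be taken as evidence in support of the hypothesis". The CI method is not named.
- **H1.2 (Safety #1)** goes the other way. Support is declared "If the 95% CI excludes values" of 10% or more.
- **H2.1B (part of Safety #2)** predicts that the proportion of supine readings at or above 140/100 mmHg will show no significant difference between droxidopa and placebo. Paired tests are run separately for systolic and diastolic pressure, "from which the 95% confidence intervals will be calculated". Then: "The presence of zero in a confidence interval will indicate a lack of statistical difference in incidence of hypertensive events".

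Neither H1.1 nor H2.1B has a minimum rate, a margin or a precision requirement. The Protocol (Study Population) expects about 40 participants in Study 1 and 25 in Study 2. The Combined protocol and SAP (item 4) gives 60 and 30. Both documents describe a pilot that is not powered for a particular effect.

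**The concern.** A CI that contains a value shows only that the data have not ruled that value out. The less data there are, the more values survive. A rule that counts survival as support therefore gives its favourable answer most readily when the study has learned least.

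For H1.1 the point wording adds a second oddity: a normalisation rate clearly above 60% also falls outside the stated form of support, although the outcome is an efficacy outcome. For H2.1B the hypothesis is itself the absence of a significant difference, so any interval wide enough to reach zero confirms it by construction. That is the weaker position for a safety outcome.

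At stake are the verdicts attached to the primary efficacy hypothesis and to one of the supine safety hypotheses. The results are meant to inform a larger trial, and a pre-stated verdict of support would be reported alongside the estimates.

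**Working it through.** The plan gives no power, error rate or sample-size derivation for these hypotheses, so there is no planned figure to reproduce. The check asks which results count as favourable, and how often.

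**H1.1: which counts are support**

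Inputs: n = 40 (Protocol) or 60 (Combined protocol and SAP); target 0.60; two-sided 95%.

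Exact (Clopper-Pearson) limits for x responders of n: lower = the 2.5% quantile of Beta(x, n−x+1); upper = the 97.5% quantile of Beta(x+1, n−x).

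| n | Counts whose CI contains 60%: exact | Wilson | Wald |
|---|---|---|---|
| 40 | 18-30 | 18-30 | 18-29 |
| 60 | 28-43 | 29-43 | 29-42 |

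18/40 = 45% has exact CI 29-62%, which contains 60%: supported. 32/40 = 80% has exact CI 64-91%, which lies above 60%: not in the stated form of support.

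**H1.1: how often support is declared**

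P(support) is the sum of the binomial probabilities C(n,x) p^x (1−p)^(n−x) over the counts in the table. The true rates p are assumptions.

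| True rate | n=40 | n=60 |
|---|---|---|
| 45% | 56% (all three methods) | 45% exact, 35% Wilson and Wald |
| 80% | 27% exact and Wilson, 16% Wald | 8% exact and Wilson, 4% Wald |

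The dependence on precision shows when p is held at 45% and n varies (exact limits): 75% at n=20, 56% at 40, 45% at 60, 18% at 100. The totals 20 and 100 are hypothetical.

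**H2.1B: how often zero stays in the CI**

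Inputs: n = 25 (Protocol) or 30 (Combined protocol and SAP). Assumptions: k participants have high supine readings on droxidopa only, each with the same proportion r of readings high, and nobody has any on placebo.

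*Paired t on each participant's difference in proportion.* Mean = rk/n and SE = r·√[k(n−k)/(n²(n−1))], so t = √[k(n−1)/(n−k)] and r cancels.

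- n=25 (critical value 2.064): k=3 gives √(72/22) = 1.81; k=4 gives √(96/21) = 2.14.
- n=30 (critical value 2.045): k=3 gives √(87/27) = 1.80; k=4 gives √(116/26) = 2.11.

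Zero is inside for k ≤ 3 at both sizes. The paired Wald ratio k/√(k−k²/n) gives the same cut: 1.85 and 2.18 at n=25, and 1.83 and 2.15 at n=30, against 1.96.

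*Exact McNemar, one yes/no outcome per participant.* Two-sided p = 2 × 0.5^k: 0.0625 at k=5 and 0.031 at k=6. The favourable verdict holds for k ≤ 5.

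With an assumed share of participants affected on droxidopa only, the probability of the favourable verdict is P(Bin(n, share) ≤ 3) to P(Bin(n, share) ≤ 5):

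| Share affected | n=25 | n=30 |
|---|---|---|
| 10% | 76% to 97% | 65% to 93% |
| 15% | 47% to 84% | 32% to 71% |

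If affected participants instead have one to six high readings at random, simulation raises the paired-t figures at 10% to 89% (n=25) and 82% (n=30).

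One concrete case: 3 of 25 participants classed hypertensive on droxidopa and none on placebo is an excess of 3/25 = 12 points. The CI is −0.7 to 24.7 points (Wald) or −1.7 to 25.7 points (paired t). The rule reads this as no difference, although excesses of more than 20 points remain compatible with the data.

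**The case against.** The best defence is that little depends on the labels. This is an openly unpowered pilot, the estimates and CIs are calculated whatever the verdict, and H2.1A separately estimates the supine SBP difference with its own CI. All of that stands and limits the harm. Pilot status excuses low power, however. It does not excuse a rule that turns low power into support, and the plan still calls these hypothesis tests.

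Nor is the H1.1 rule empty. With exact limits, support is declared with probability about 97% at a true 60%, against 31% (n=40) or 18% (n=60) at a true 40%. The expectation of 25 responders among about 40 (62.5%) shows that 60% already works as a planning value. That favours calling it one rather than testing against it.

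The assumed 10% may also be too high. Screening excludes sustained BP of 140/100 mmHg or more, supine or seated, and the Study 1 section adds that "Individuals who do not respond to droxidopa with a normal seated SBP will be excluded from Study 2". A lower share only makes the favourable H2.1B verdict more likely, while leaving less excess to miss.

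A reader might infer three stronger things that the documents do not support:

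- *That an interval wholly above 60% will be declared a failure.* The plan says only what counts as support; such a result falls outside it.
- *That H2.1B will be presented as proof of supine safety or equivalence.* The text claims only a lack of statistical difference.
- *That repeated readings will be analysed as if independent.* The plan specifies dependent proportions, and the Preliminary Data give proportions of recordings as mean ± SD, which suggests one value per participant. A pooled percentage of all recordings appears there too, so the unit needs stating, but no error is shown.

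**Conclusion.** The concern holds for the two decision rules as written. Both let imprecision produce the favourable verdict, in contrast to H1.2 in the same section. For H1.1, observed rates from 45% to 75% (n=40) or 46.7% to 71.7% (n=60) count as support with exact limits, and the direction is the same for Wilson and Wald intervals. For H2.1B, a true excess affecting 10% of participants would more often than not be read as no difference at either planned size. The exact probabilities rest on the assumed true rates, on no hypertension under placebo, on equal numbers of high readings among those affected, and on a CI method that the plan does not name.

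This should be corrected before analysis, but it is not a threat to the trial. It would go too far to say that the pilot's conclusions or the larger trial turn on these rules, because the documents tie no go/no-go decision to either verdict.

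**What to change.** **H1.1.** Delete the rule that inclusion of 60% is support. State the aim as estimating the normalisation rate, with 60% as the anticipated value, and report the proportion with a 95% CI by a named method. If a verdict is wanted, require the lower limit to exceed a minimum rate that the sponsor justifies; the documents give none.

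**H2.1B.** Delete the reading of zero in the CI as lack of difference. Report the paired droxidopa-placebo difference in each participant's proportion of supine readings at or above threshold, separately for systolic and diastolic, with a 95% CI. Claim no important excess only if the upper limit is below a pre-stated margin that the sponsor justifies. In one line, state that the participant is the unit of analysis.

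**Cost.** The data and sample size do not change, and the estimation version is a wording change only. H2.1B will probably be reported as an estimate rather than as confirmed. Rules that require exclusion are demanding at these sizes: with exact limits, H1.2 is met only by 0/40 (upper limit 8.8%) or at most 1/60 (8.9%). For H1.1, purely illustrative minimum rates of 33%, 40% and 50% would need at least 20, 23 and 27 of 40 responders, with power at a true 60% of 93%, 69% and 21%. With 60 participants they would need 28, 33 and 39, with power 99%, 82% and 26%.
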